Efficacy of Kinesio Taping in Musculoskeletal Neck Pain in Short and Medium Term. A Randomized Control Double Blinded Clinical Trial

TITLE: Efficacy of Kinesio Taping in Musculoskeletal Neck Pain in Short and Medium Term. A Randomized Control Double Blinded Clinical Trial

INVESTIGATOR PRINCIPAL: [name]

PROJECT ENTITIES: COMPLUTENSE UNIVERSITY OF MADRID & NURSERY, PHYSIOTHERAPY AND PODIATRY FACULTY.

NUMBER OF IDENTIFICATION:

DATE: 1ST JUNE 2021.

STUDY PROTOCOL

Type of Study: A double-blind controlled clinical trial was conducted with 30 days following.

Target population: Population with musculoskeletal neck pain.

Sample: A convenience sampling will be carried out among the patients according to eligibility criteria.

Inclusion criteria:

- Age between 18 and 30 years old,
- Presence of myofascial pain syndrome (MPS) and myofascial trigger point (MTP) in the upper trapezius muscle, according to the diagnostic criteria proposed by the American Academy of Pain Medicine and the scientific community a) tender point on palpation, with or without referred pain b) patient recognizes pain during tender point palpation c) at least three of the following: muscle stiffness or muscle spasm, limited range of motion in an associated joint, increase of pain with stress, palpation of tight band and / or nodule, associated with a tender point

- Understand written Spanish.

Exclusion Criteria:

- Neck pain of traumatic origin, due to recent surgery or causing radiculopathy.
- Have been diagnosed with chronic pathology, as well as neoplastic or suspicion of it.
- Have received some type of pharmacological or non-pharmacological analgesic treatment in the last 30 days
- Pregnant or menstrual women.

Sample size

The required sample size was calculated using the G * Power software (G * Power version 3.1.9.6). To identify the differences between the 3 intervention groups at the 3 evaluation moments, the sample size was estimated based on finding a moderate effect size (Cohen's $f = 0.25$). Considering an alpha error of 5% (0.05) and a beta error of 10% (statistical power of 0.9), he estimated the need for a sample size of at least 45 patients in total.

Procedure

During the months of May to July 2021, a research assistant will contact potential participants who will be invited to participate in this study. Once they agree to participate, it will schedule for a face-to-face consultation at the university, where the main researcher will inform the study participants. Once the information sheet and informed consent will be a sign, an investigator will carry out the

measurements of the variables for initial data collection in the first session. In another room, an expertise physiotherapist with experience in applying Kinesio taping will perform interventions on patients on the same day as the initial evaluation. In this way, the investigator that will assess outcomes will be blind to the treatment that each patient will receive.

At the second consultation, 4 days after the first, the same physiotherapist who applied the bandage will remove it from the patients who will receive it and any remains of the bandage on the skin were cleaned. For patients in the control group (nothing apply), it will be the same protocol to alter not the double-blind. The principal investigator will perform the evaluations and data collection without knowing the intervention the patient will receive. In a third consultation, as a follow-up (30 days after the second consultation), the collection of the same measurements and clinical variables from the patients who completed the process will repeat by the same investigator that did the outcomes' assessment.

The information sheet, the informed consent, and the evaluation instruments will be collected by a researcher, stored, and guarded in the Department of Radiology, Rehabilitation and Physiotherapy of the Complutense University of Madrid. Thus, complying with the provisions of Organic Law 3/2018, of December 5, on the Protection of Personal Data and guarantee of digital rights.

Ethical Aspects

The study has the approval of the research commission of the Faculty of Nursing, Physiotherapy and Podiatry of the Complutense University of Madrid. Also, with the favorable opinion of the research commission of the Hospital Clinico San Carlos, Madrid. Lastly, it will be evaluated by the Ethics Committee of the research institute Hospital Clinico San Carlo Madrid, Instituto de investigación Sanitaria Hospital Clínico San Carlos (IdISSC).

The study will comply with all the ethical principles of the Declaration of Helsinki. All participants will participate in the study on a voluntary basis. They will be informed of the objective of the study, the procedure, and the process of carrying it out. In addition, the informed consent of each participant and their guardians will be required, which may be revoked at any time. In addition, they are within their right to know the results of the investigation once it has been completed.

The clinical and personal information will be totally confidential where the researchers will comply with the confidentiality commitments of the hospital center and the Faculty of Nursing, Physiotherapy and Podiatry. The treatment, communication and transfer of personal data of all participating subjects will comply with the provisions of the General Regulations for the Protection of Personal Data (Regulation 2016/679 of the European Parliament) and Organic Law 3 / 2018, of December 5, Protection of Personal Data and guarantee of digital rights.

Therefore, it is considered that carrying out the study complies with the ethical and research standards and that the benefits in knowledge in the field that can

Efficacy of Kinesio Taping in Musculoskeletal Neck Pain in Short and Medium Term. A Randomized Control Double Blinded Clinical Trial. [name] et al. 1 June 2021. University Complutense of Madrid.

be derived from it could significantly improve the healthcare activity, not assuming the realization of this, a serious damage to patients, families or professionals.

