Efficacy of Kinesio Taping in Musculoskeletal Neck Pain in Short and Medium Term. A Randomized Control Double Blinded Clinical Trial

TITLE: Efficacy of Kinesio Taping in Musculoskeletal Neck Pain in Short and Medium Term. A Randomized Control Double Blinded Clinical Trial

INVESTIGATOR PRINCIPAL: [name]

PROJECT ENTITIES: COMPLUTENSE UNIVERSITY OF MADRID & NURSERY, PHYSIOTHERAPY AND PODIATRY FACULTY.

NUMBER OF IDENTIFICATION:

DATE: 1ST JUNE 2021.

Statistical Analysis Plan

The statistical software IBM SPSS® (Statistical Package for the Social Sciences 22, SPSS Inc., Chicago, IL USA) was used. The quantitative variables were presented as mean \pm standard deviation (SD), while the qualitative variables were shown as an absolute value (relative frequency percentage). To study the effects produced on the main variables of each intervention at different times of evaluation, an analysis of variance of repeated measures (factorial ANOVA) was applied. Secondarily, the same analysis was performed for each intervention on the secondary variable.

Additionally, the effect size (partial eta squared, η^2) was calculated for the changes produced by comparing within the same intervention group (intragroup) and comparing between intervention groups (intergroup), following the classification criteria described by Cohen: small (0.1 - 0.24), moderate (0.25 - 0.39), and large (> 0.4)

The interpretation of the statistical tests was performed based on a significance level of 5% ($p < 0.05$) for a 95% confidence interval.

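### The 45 patients reproduce as 0.9 power for a group-by-visit interaction at f = 0.25, but on that scale the effect is about 1.1 SD in change for one arm, so calling it moderate misleads

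*Protocol*

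**What the plan says.** The Sample size section of the protocol names G*Power 3.1.9.6 and gives the aim as "To identify the differences between the 3 intervention groups at the 3 evaluation moments". It says that "the sample size was estimated based on finding a moderate effect size", with Cohen's f = 0.25 in brackets. Alpha is 0.05 and power 0.9, and the section concludes "he estimated the need for a sample size of at least 45 patients in total".

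It does not give the term tested, the G*Power effect-size option, the correlation between visits, the sphericity correction, the allocation ratio, or any outcome SD or clinical difference.

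The SAP plans a repeated-measures factorial ANOVA without naming the term of interest. It will report partial eta squared for changes within a group and for "comparing between intervention groups (intergroup"), with cut-offs of 0.1, 0.25 and 0.4 for small, moderate and large.

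**The concern.** A Cohen's f in a three-group, three-visit design has no single meaning. The same 0.25 can describe a time effect, a group effect or an interaction. For the interaction it can be scaled by the SD at one visit or by the residual of the repeated-measures model. These readings need very different numbers of patients, and 45 is near the low end.

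What is at stake is how a null result is read. A reader told that the trial has 0.9 power for a moderate effect will take non-significance as fair evidence against one. If the 0.9 belongs to a much larger effect, that inference fails, and the inputs needed to notice this are not in the protocol.

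**Working it through.** **Inputs from the documents.** k = 3 groups, m = 3 visits, f = 0.25, alpha = 0.05, target power 0.9, N = 45.

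**Assumed, because not stated.** Correlation rho = 0.5, epsilon = 1, equal arms.

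**1. Reproduce 45.** For the group-by-visit interaction on the G*Power default scale, lambda = f² × N × m / (1 − rho) = 0.0625 × 45 × 3 / 0.5 = 16.875. The df are (k − 1)(m − 1) = 4 and (N − k)(m − 1) = 84. The noncentral F gives power 0.911. At N = 42 it is 0.887, so 45 is the smallest multiple of three that reaches 0.9.

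**2. Other readings of f = 0.25 do not give 45** (smallest multiple of three for 0.9 power):

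| Reading | N needed | Power at 45 |
|---|---|---|
| Interaction, default scale | 45 | 0.911 |
| Time effect (compares no groups) | 36 | 0.96 |
| Interaction, lambda = f² × N × (m − 1) | 126 | 0.42 |
| Interaction, partial-eta-squared scale | 129 | 0.39 |
| Between-group term | 141 | 0.41 |
| One-way ANOVA | 207 | 0.28 |

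The test and scale are therefore a fair inference. Rho and epsilon are less certain. With lambda and both df multiplied by epsilon, rho = 0.6 and epsilon = 0.75 give lambda 15.82 on 3 and 63 df, power 0.914 (0.892 at N = 42), which also returns 45.

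**3. Convert to partial eta squared.** From lambda and the error df: 16.875 / (16.875 + 84) = 0.167, so f = √(16.875/84) = 0.45. In population terms, f² × m / [(1 − rho)(m − 1)] = 0.1875, so eta squared = 0.1875 / 1.1875 = 0.158 and f = √0.1875 = 0.43. Both values of f are above 0.4.

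**4. Convert to an arm difference.** On the default scale f is the root mean square of the double-centred cell means divided by the SD at one visit. If one arm shifts by d SD at both follow-ups and the others do not, f = √(2/9) × √(2/9) × d = 0.222d. So f = 0.25 means d = 0.25 / 0.222 = 1.125. At rho = 0.5 the SD of change is √(2 × 0.5) = 1 outcome SD, so this is also 1.125 SD of change. For other patterns, the largest arm difference in change from baseline at f = 0.25 is:

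- evenly graded arms, sustained effect: 1.30 SD
- evenly graded arms, linear time course: 1.50 SD
- one arm sustained and one transient: 0.92 SD
- one arm early only and another late only: 0.71 SD (1.42 SD between the two follow-ups)
- one arm crossing from above to below the others: 0.65 SD (1.30 SD between the two follow-ups)

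**5. Power at N = 45 for conventional moderate effects.** Each line is a separate definition.

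- One arm differing by 0.5 SD at both follow-ups: f = 0.222 × 0.5 = 0.111. At rho 0.5, lambda = 3.33 and power is 0.26. At rho 0.3, lambda = 2.38 and power is 0.19. At rho 0.7, lambda = 5.56 and power is 0.42.
- f = 0.25 on the partial-eta-squared scale: lambda = 0.0625 × 84 = 5.25, power 0.39.
- Between-group term, f = 0.25: lambda = 0.0625 × 45 × 3 / (1 + 2 × 0.5) = 4.22 on 2 and 42 df, power 0.41.

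**6. Sensitivity of the stated power.** With f = 0.25 on the default scale, power at 45 is 0.78 at rho 0.3, 0.85 at 0.4, 0.96 at 0.6 and 0.99 at 0.7. At rho 0.5 it is 0.84 if epsilon is 0.75 and 0.71 if epsilon is 0.5.

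**The case against.** The strongest reply is that nothing is miscalculated. The protocol names its program and defines moderate as f = 0.25, and the program returns 45. That stands: a reader might infer an arithmetic error, and there is none.

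A reader might also infer that 1.1 SD is a floor. It is not. The 1.125 SD figure is the smallest difference only when the arms share one time profile. With visits at baseline, at tape removal and 30 days later, differing profiles are plausible, and some give 0.9 power at smaller differences from baseline. Likewise 0.26, 0.39 and 0.41 are not one range, since they answer three different questions. At 0.5 SD the interaction power runs from 0.16 to 0.38 over common patterns, and is 0.60 to 0.69 for opposing time courses. A higher correlation helps: at rho 0.7 a 0.8 SD difference in one arm has power 0.85, against 0.61 at rho 0.5. None of the 0.5 SD patterns computed at rho 0.5 reaches 0.9, nor does the one-arm pattern over rho 0.3 to 0.7.

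Finally, the SAP literally calls a partial eta squared of 0.25 to 0.39 moderate. At 0.25, lambda = (0.25/0.75) × 84 = 28 and power is 0.99. This does not rescue the protocol's claim. The protocol attaches 0.25 to Cohen's f, and the SAP places the same number on eta squared, which is a different scale and a separate defect.

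**Conclusion.** The sample size is reproducible, but its description is misleading. The 0.9 power belongs to an interaction of about 0.16 to 0.17 in partial eta squared (f about 0.43 to 0.45 on that scale, above the 0.4 mark for a large f), or about 1.1 SD in change for one arm against two equal arms. For the conventional moderate effects in step 5, power ranges from 0.19 to 0.42 depending on the definition and the correlation.

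This rests on an inferred test, effect-size scale, correlation, epsilon and equal allocation; only the sponsor can confirm them. The documents do not themselves say that a null result would rule out a moderate effect. That is an inference a reader might draw from the stated power. Nor does the point show that 45 is the wrong number to enrol. It should be corrected, as a matter of reporting and interpretation.

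**What to change.** Keep 45. In the Sample size section:

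- State that the calculation is for the group-by-visit interaction on the G*Power default effect-size scale, and name that term in the SAP as the one the trial is sized for.
- Have the sponsor confirm and report the correlation, epsilon and allocation ratio actually used.
- Replace the word moderate with the detectable difference: about 1.1 SD in change for one arm against the other two at correlation 0.5, partial eta squared about 0.16.
- Give the power for a 0.5 SD difference in that same pattern: 0.19, 0.26 and 0.42 at correlations 0.3, 0.5 and 0.7.
- State that a non-significant result does not exclude a moderate effect.

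If the confirmed inputs differ from those assumed here, recompute these figures before inserting them. The cost is wording and a less favourable stated power. No extra patients and no change of analysis are needed.

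### No recording or analysis of harms or early tape removal is planned, and the only post-treatment data collector described is the assessor who must stay blind

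*Protocol*

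**What the plan says.** The protocol's Procedure section separates treatment from assessment. On treatment: "In another room, an expertise physiotherapist with experience in applying Kinesio taping will perform interventions on patients". The purpose is that "the investigator that will assess outcomes will be blind to the treatment that each patient will receive".

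At the second consultation, four days later, "the same physiotherapist who applied the bandage will remove it from the patients who will receive it and any remains of the bandage on the" (the sentence ends with cleaning of the skin). Control patients, to whom nothing is applied, go through the same visit procedure so that blinding is not disturbed. For outcome measurement at that visit: "The principal investigator will perform the evaluations and data collection without knowing the intervention the patient will receive". At the third consultation, 30 days after the second, the measurements are taken again "from the patients who completed the process will repeat by the same investigator that did the outcomes' assessment".

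No sentence gives the physiotherapist anything to record. Neither document mentions adverse events, skin reactions, tolerability or tape removed before day 4. The SAP covers main variables and a secondary variable, names none of them, and contains no safety analysis.

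**The concern.** The intervention is an adhesive product worn on the skin for four days. A reader of the results will want to know how many patients in each arm had a skin reaction and how many took the tape off early. The second question also bears on efficacy, because a patient who removed the tape on day 2 did not receive the four-day intervention. If neither is written down at the time, no later analysis can recover it.

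The division of roles adds a second problem. The person who sees the skin has no recording task, and the person who records must not learn the allocation. A patient who mentions itching or peeling tape to the assessor has shown that tape was applied. Only taped patients can make such a remark, so in the comparison with no tape the loss of blinding falls on one side.

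**Working it through.** **Roles after treatment, as the Procedure section describes them**

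| Step | Who | Knows allocation? | Recording task stated? |
|---|---|---|---|
| Application, visit 1 | Physiotherapist, separate room | Yes | None |
| Removal and skin cleaning, visit 2 (day 4) | Same physiotherapist | Yes | None |
| Evaluation, visit 2 | Principal investigator | Must not | Yes, outcomes |
| Evaluation, visit 3 (30 days after visit 2) | Same outcome assessor | Must not | Yes, same measurements |

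The one contact at which tape and skin are certain to be inspected by someone who may know the arm produces no data. Every contact that produces data belongs to someone who may not know the arm. That removal precedes the visit 2 evaluation is inferred from the order of the text.

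**The plan's own figure.** The only design figure is the total of 45 (protocol, Sample size). The stated inputs are 3 groups, 3 times, f = 0.25, alpha 0.05 and power 0.90. I assume correlation 0.5 between times and sphericity, neither of which is stated. For the group-by-time interaction:

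- lambda = f² × N × m / (1 − rho) = 0.0625 × 45 × 3 / 0.5 = 16.875
- df1 = (3 − 1)(3 − 1) = 4; df2 = (45 − 3)(3 − 1) = 84
- power = 0.911 at N = 45 and 0.887 at N = 42

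So 45 reproduces. The point does not depend on it; it is used only to see what harms data could show.

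**What collected data could show.** Equal allocation is assumed, giving 45/3 = 15 per arm. If two arms wear tape (also an assumption), 30 patients are taped.

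One-sided 95% upper limit with zero events = 1 − 0.05^(1/n):

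- n = 15: 1 − 0.05^(1/15) = 18.1%
- n = 30: 1 − 0.05^(1/30) = 9.5%

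Chance of seeing at least one reaction if the true rate were 5% (illustrative) = 1 − 0.95^n:

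- n = 15: 0.54
- n = 30: 0.79

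The data would therefore be descriptive. Without collection there is no numerator, and no limit can be given at all.

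**The case against.** The strongest reply is that the protocol names no outcome variables and the SAP names neither its main nor its secondary ones, so silence on harms is part of a general silence. Nothing forbids the physiotherapist from making a note, and a patient with sore skin would naturally tell the person taking the tape off. Blinding is also exposed in other ways: untaped patients know they are untaped, and anyone may say so with or without a reaction.

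Much of this stands, and it limits the point in three ways. What can be said is that no harms collection or analysis is planned, not that none could occur; the consent pages are not available to check. A reader might infer that every reaction must either be lost or reach the assessor, but the documents do not establish that, since an informal note by the physiotherapist is possible. And a complaint voiced to the assessor adds an amount that cannot be quantified to an existing exposure. The documents give no complaint rate from which to estimate how many assessments would be unblinded.

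A reader might also see a contradiction with Ethical Aspects, which describes the study as "not assuming the realization of this, a serious damage to patients, families or professionals". That sentence is an ethical judgement made before the trial about conducting the study, and it concerns serious damage. It is not a safety result that the trial must support. A form recording skin findings in arms of about 15 could neither confirm nor refute it.

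What the reply does not remove is that no duty, form, variable or table exists for reactions or early removal, and an informal note is not something that can be reported by arm.

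**Conclusion.** The point holds as a gap in the plan that is cheap to close and should be closed. Followed as written, the trial cannot report skin reactions or early tape removals by arm. The described arrangement also leaves the blinded assessor as the only person with a data collection role after treatment.

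The unblinding risk is shown only for tape versus no tape. The other arms are not described, so nothing can be said about whether a reaction would distinguish between them.

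The gain should not be overstated. With zero events the one-sided 95% upper limit would be 18.1% for 15 patients (equal allocation assumed) or 9.5% for 30 (two taped arms assumed as well). The case for recording is that these data cannot be obtained afterwards, not that they would settle the safety of the tape.

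**What to change.** - **Recording at visit 2.** Before the blinded assessment, the physiotherapist completes a short form for every patient in every arm: skin findings at the site (present or absent, and type), whether the tape was still in place where one was applied, and the date and reason for any earlier removal. The form is kept from the assessor. Control patients already go through the same visit procedure, so it can be completed for them too.
- **Patient instruction.** Patients are asked to raise anything about the application with the physiotherapist and not with the assessor. A route for urgent complaints to reach the study team must stay open, because the visit 2 assessor is the principal investigator.
- **SAP.** Add a descriptive table of events and early removals by arm with exact confidence intervals, and state that it is descriptive only.
- **Visit 3, optional.** A question about events since visit 2, asked by someone who is not blind, would be useful. The protocol places only the assessor at that visit, so this needs an extra person.

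The cost is one form, one sentence of patient instruction, one table, and a few minutes of physiotherapist time per patient. The optional visit 3 question costs more. None of this sets a treatment or stopping rule; it settles only who records what and how it is reported.

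### The no-tape comparison is labelled double-blind but is only assessor-blind, so by itself it cannot support a specific taping effect

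*Protocol*

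**What the plan says.** The protocol's Type of Study reads "A double-blind controlled clinical trial was conducted with 30 days following", and the titles of both documents carry the same label (SAP: "A Randomized Control Double Blinded Clinical Trial").

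The Procedure section says how masking is achieved:

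- **Assessor, first session.** Treatment is given in a separate room, so that "the investigator that will assess outcomes will be blind to the treatment that each patient will receive".
- **Assessor, second consultation.** "The principal investigator will perform the evaluations and data collection without knowing the intervention the patient will receive".
- **Physiotherapist.** Tape removal is set for day 4, and the person responsible is specified: "the same physiotherapist who applied the bandage will remove it from the patients who will receive it".
- **Untaped patients.** "For patients in the control group (nothing apply), it will be the same protocol to alter not the double-blind".

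The Sample size section refers to "the differences between the 3 intervention groups at the 3 evaluation moments", but the no-tape control is the only arm whose content is described. The SAP sets out its analysis "To study the effects produced on the main variables of each intervention at different times of evaluation", by repeated-measures factorial ANOVA with effect sizes within and between groups. It does not distinguish contrasts by who is masked.

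**The concern.** The protocol presents the shared day-4 routine as preserving the double blind for the no-tape arm. That routine may hide allocation from the assessor. It cannot hide from a patient that no tape was worn. The label is therefore attached to the one contrast in which patient blinding is impossible.

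A tape-versus-nothing difference combines any specific effect of the tape with expectation. The SAP's group-by-time test pools all arms, so a tape-versus-nothing difference alone can make it significant. A reader who sees a title that pairs efficacy with double blinding may assume that expectation is controlled in every comparison, and nothing in the SAP warns otherwise.

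**Working it through.** **1. Who is masked in the no-tape contrast**

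| Role | What the protocol describes | Masked? |
|---|---|---|
| Outcome assessor | Treatment in another room; evaluates without knowing the intervention | Yes, as described |
| Physiotherapist | Applies and removes the tape | No |
| Patient with no tape | Nothing applied; same day-4 routine | No |

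Under Ethical Aspects, participants are told the objective and procedure. No section describes concealing tape versus no tape from them. One role is masked, so the contrast is assessor-blind.

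**2. The plan's own sample size**

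Inputs from the protocol: 3 groups, 3 visits, f = 0.25, alpha 0.05, power 0.90, N = 45. Assumed because not stated: correlation between visits ρ = 0.5, sphericity, equal groups. For the group-by-time interaction:

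- λ = f² × N × m / (1 − ρ) = 0.0625 × 45 × 3 / 0.5 = 16.875
- df = (3 − 1)(3 − 1) = 4 and (45 − 3)(3 − 1) = 84
- power = 0.911, and 45 is the smallest equal-group total that reaches 0.90.

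The stated 45 is reproduced. This supports reading the group-by-time interaction as the intended test, although the SAP does not name it.

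**3. Illustration: how often expectation alone makes that test significant**

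Every input here is an assumption: zero specific effect; SD 1; compound symmetry; equal allocation; one untaped arm; and all other arms taped and shifted by b at both post-baseline visits, with b = 0.2 to 0.5 and ρ = 0.3 to 0.7.

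Three arms: taped means are (0, b, b) and untaped means are (0, 0, 0). After removing arm and visit averages, the interaction effects are:

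- each taped arm: (−2b/9, b/9, b/9), sum of squares 6b²/81
- untaped arm: (4b/9, −2b/9, −2b/9), sum of squares 24b²/81
- total: (2 × 6 + 24)b²/81 = 4b²/9

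λ = n per arm × 4b²/9 / (1 − ρ). With n = 15, ρ = 0.5 and b = 0.3, λ = 15 × 0.04 / 0.5 = 1.20. With df 4 and 84:

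| ρ | b = 0.2 | b = 0.3 | b = 0.5 |
|---|---|---|---|
| 0.3 | 6.9% | 9.4% | 18.9% |
| 0.5 | 7.6% | 11.4% | 25.6% |
| 0.7 | 9.6% | 16.4% | 41.5% |

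If the control is additional to the three intervention groups, there are four arms and the total becomes b²/2. The ranges over the same b and ρ are:

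- 45 split evenly (11.25 per arm, df 6 and 82): 6.2% to 29.3%
- whole arms of 11 or 12 (df 6 and 80, or 6 and 88): 6.2% to 31.4%
- 15 per arm (df 6 and 112): 6.6% to 39.7%

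A simulation of 20,000 trials per cell, for three arms of 15 and four arms of 11, 12 and 15, agrees within 0.6 percentage points. With b = 0 it gives 4.8% to 5.4%, against the nominal 5%.

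**The case against.** The strongest reply is that the documents contain an imprecise label and no stated wrong inference. A no-treatment arm is legitimate, and no section says that a tape-versus-nothing difference will be read as a specific effect. The sentence about the control group is followed directly by the one on assessor masking, so masking the assessor may be all it was meant to do. An undescribed arm could be sham tape, in which case some contrast may deserve the label. What patients were told about the arms would be in the information sheet, which is not in the available text. The percentages rest on assumed shifts and correlations, and on every other arm being taped.

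Most of this is right, and it limits the point. The documents do not announce an over-reading, the size of any expectation effect is unknown, and the label cannot be called wrong for the whole trial. But a sham arm elsewhere would not blind patients who wear nothing. Whatever its purpose, the sentence on the control group claims for the no-tape contrast a property that it lacks. How much patients expected from tape affects the size of the bias, not the mismatch.

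**Conclusion.** The concern holds. Any tape-versus-nothing contrast in this trial is assessor-blind only. It can support a statement about the overall effect of being taped, but not by itself a specific taping effect. The conclusion on masking follows from the protocol's own description and needs no assumption. It does not extend to contrasts between other arms, whose content is not given.

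The size of the consequence cannot be established from the documents, which name no outcomes and give no shift, correlation or allocation ratio. Under the assumptions above, expectation alone makes the 5% group-by-time test significant in 6.2% to 41.5% of trials across the layouts considered. These are false-positive rates only if significance is read as a specific effect; for the overall effect of being taped, they are power. For an outcome that expectation cannot influence, the excess over 5% could be near zero. The data remain usable, but the label and the permitted claim should be corrected.

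**What to change.** - **Titles, Type of Study and Procedure:** describe the no-tape comparison as assessor-blind. Keep the double-blind label only for a contrast, if one exists, in which both arms wear tape and patients are not told which. Naming the arms, and who is masked in each comparison, would settle where the label belongs.
- **SAP:** state that no-tape contrasts are patient-unblinded and include expectation effects. State also that neither such a contrast nor a significant omnibus group-by-time test alone will be taken as evidence of a specific taping effect.

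The cost is wording in two documents, with no change to sample size, visits or test. The price is a less favourable design label and a narrower claim. If no tape-versus-tape contrast exists, the trial can make no specific-effect claim.
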